For each of the clinical response, the odds ratio, corresponding 95% confidence intervals and p-value will be provided by using a logistic regression model with the baseline, and the treatment-by-baseline interaction as covariates. Odds Ratio is showing the strength of the association between the treatment effect and the clinical response.

Odds Ratio =
$$(p_1/(1-p_1)) / (p_2/(1-p_2))$$

Where

p₁ = proportion of responder of ISIS 721744 80 mg every 4 weeks (or every 8 weeks)

 p_2 = proportion of responder of the pooled Placebo

Odds Ratio ranges from 0 to infinity. When Odds Ratio = 1, there is no association; when Odds Ratio > 1, patients in the active treatment group are more likely than patients in the placebo group to be responders.

The responder is derived based on time-adjusted Investigator-confirmed HAE attack rate per every-4-week. For patients who discontinued the Treatment Period early and started OLE, and patients who discontinued the Treatment Period early and were lost to follow-up before Week 25, the HAE attack rate per every-4-week for each treatment group is considered as the same before and after withdrawal.

Main analysis will be based on FAS.

Sensitivity Analysis

To evaluate the robustness of inferences made on the main analysis, a sensitivity analysis on FAS will be performed based on imputed data by using MI methods assuming J2R which is described in Section 4.9.1.3. For each imputed data set, the percentage reduction will be calculated and main analysis described above will be performed. Results will be combined using Rubin's rules.

4.9.3.4. Percentage of Investigator-Confirmed Hereditary Angioedema (HAE) Attack-Free Patients from Week 5 to Week 25

The clinical response of Investigator-confirmed HAE attack-free from Week 5 to Week 25 will be analyzed using the same method as described for clinical responses in Section 4.9.3.3.

For patients who discontinued the Treatment Period early and started OLE, and patients who discontinued the Treatment Period early and were lost to follow-up before Week 25, the HAE attack rate per every-4-week for each treatment group is considered as the same before and after withdrawal.

Main analysis will be based on FAS and PPS.

TP-GDO-WW-016-08 Effective Date: 26 Nov 19 Related to: SOP-GDO-WW-019 CONFIDENTIAL Project Document Version No. 2.0

Project Document Effective Date: 13 Dec 2023 Page 34 of 61

Sensitivity Analysis

To evaluate the robustness of inferences made on the main analysis, a sensitivity analysis on FAS will be performed based on imputed data by using MI methods assuming J2R which is described in Section 4.9.1.3. For each imputed data set, the percentage reduction will be calculated and main analysis described above will be performed. Results will be combined using Rubin's rules.

4.9.3.5. Number of Investigator-Confirmed Hereditary Angioedema (HAE) Attacks Requiring Acute Therapy from Week 5 to Week 25

HAE attacks requiring acute therapy include those attacks with the following concomitant medication.

C1 Esterase Inhibitors (human)	Berinert
	Cinryze
C1 Esterase Inhibitor (recombinant)	Ruconest
Plasma Kallikrein Inhibitor (human)	Kalbitor (ecallantide)
Bradykinin antagonist	Firazyr (icatibant)

The time-normalized number of Investigator-confirmed HAE attacks (per every-4-week) requiring acute therapy from Week 5 to Week 25 will be analyzed using the same methods as described for the primary efficacy endpoint in Sections 4.9.2.1, 4.9.2.2 and 4.9.2.4.

Main analysis will be based on Poisson regression model on FAS with treatment policy strategy. For patients who discontinued the Treatment Period early and started OLE, and patients who discontinued the Treatment Period early and were lost to follow-up before Week 25, will have the time-adjusted attack rate included in the analysis.

Sensitivity Analyses

A NB regression on FAS will be performed as a sensitivity analysis.

To evaluate the robustness of inferences made on MAR, a sensitivity analysis based on FAS will be performed based on imputed data by using multiple imputation (MI) methods assuming J2R which is described in Section 4.9.1.3. For each imputed data set, the Poisson regression model used for the primary analysis will be performed. Results will be combined using Rubin's rules .

4.9.3.6. Percent of Patients who are Well-Controlled on the Angioedema Control Test (AECT) at Week 25

The AECT is a validated patient-reported outcome instrument to assess disease activity in patients with recurrent angioedema (Weller *et al.* 2020) which will be assessed during Treatment and Post-Treatment Periods as outlined in Protocol Appendix A. The questionnaire consists of four questions asking about the frequency and severity of angioedema experienced in the last 4 weeks. Each question has 5 response choices. Scored as the following:

TP-GDO-WW-016-08 CONFIDENTIAL Project Document Version No. 2.0 Effective Date: 26 Nov 19 Project Document Effective Date: 13 Dec 2023 Related to: SOP-GDO-WW-019 Page 35 of 61

1. How often have you had angioedema?	Very often = 0, Often = 1, Sometimes = 2, Seldom = 3, Not at all =4
2. QOL been affected by angioedema?	Very much = 0, Much = 1, Somewhat = 2, A little = 3, Not at all =4
3. Unpredictability of angioedema?	Very much = 0, Much = 1, Somewhat = 2, A little = 3, Not at all =4
4. Angioedema been controlled?	Not at all = 0, A little = 1, Somewhat = 2, Well = 3, Very well =4

The AECT total score is the summation of scores of 4 questions and can be used to identify patients with poorly controlled disease by working with a cutoff value of greater than or equal to 10 points. Patients with the total score less than 10 points (0–9) in the AECT have poorly controlled disease whereas patients with controlled disease score 10–16 points. The AECT will be completed by the patient.

The number and percentage of patients who are well-controlled on the AECT at Week 25 will be summarized by treatment group.

The clinical response of well controlled patients on AECT at Week 25 will be analyzed on all patients with at least one non-missing AECT value at a post-baseline visit, using the same method as described for clinical responses in Section 4.9.3.3. However, the baseline and treatment-by-baseline interaction is not included for AECT (i.e., no covariates in the logistic regression).

For patients who discontinued the Treatment Period early and started OLE, and patients who discontinued the Treatment Period early and were lost to follow-up before Week 25, before calculating the responder of well controlled on the AECT at Week 25, missing AECT total score will be imputed by LOCF which is described in Section 4.9.1.3.

Sensitivity Analyses

To evaluate the robustness of inferences made on the imputed data using LOCF, a sensitivity analysis on all patients with at least one non-missing AECT value at a post-baseline visit will be performed based on imputed data by using MI methods assuming J2R which is described in Section 4.9.1.3. For each imputed data set, the responder will be derived, and main analysis described above will be performed. Results will be combined using Rubin's rules.

A sensitivity analysis on all patients with at least one non-missing AECT value at a post-baseline visit based on imputed data by using LOCF in Section 4.9.1.3 will also be performed. In the sensitivity analysis, the logistic regression will include the baseline AECT total score (continuous) as a covariate. Missing baselines will be imputed first by the average of available baselines across all patients in the FAS.

4.9.3.7. Change from Baseline in Angioedema Quality of Life (AE-QoL) Questionnaire Total Score at Week 25.

Quality of life will be assessed by the AE-QoL questionnaire during Screening, Treatment, and Post-Treatment Periods as outlined in Protocol Appendix A.

TP-GDO-WW-016-08 CONFIDENTIAL Project Document Version No. 2.0 Effective Date: 26 Nov 19 Project Document Effective Date: 13 Dec 2023 Related to: SOP-GDO-WW-019 Page 36 of 61

The AE-QoL questionnaire is a validated tool to assess symptom specific health-related quality of life impairment in patients suffering from recurrent angioedema (Weller *et al.* 2012). The AEQoL is a self-administered questionnaire that can be completed in less than 5 minutes; it comprises 17 questions across 4 domains: functioning, fatigue/mood, fears/shame, and food. Each domain includes the following questions:

Functioning	How often have been restricted in the area of Q1. Work; Q2. Physical activity; Q3. Leisure time; Q4. Social relations
Fatigue/mood	Q6. Difficulty falling asleep; Q7. Wake up during the night; Q8. Tired since not sleeping well; Q9. Trouble on concentrating; Q10. Depressed
Fears/shame	Q12. Swelling episode burden you; Q13. Afraid swelling could occur suddenly; Q14. Afraid frequency of the swelling increase; Q15. Ashamed to go out in public because of swelling; Q16. Embarrassed or self-conscious because of swelling; Q17. Afraid treatment has negative long-term effects
Food	Q5. Restrict eating and drinking; Q11. Limit your choices of food/beverage

The AE-QoL can be used to calculate scores for the 4 individual domains and can also be used to determine a total score. The AE-QoL will be completed by the patient.

AE-QoL will be evaluated by determining its four individual domain scores and a total score. Each item answered by the patient scores between 0 and 4 points depending on the answer option chosen by the patient: Never = 0, Rarely = 1, Occasionally = 2, Often = 3, Very often = 4. The AE-QoL domain scores and total score are calculated by using the following formula:

(Sum score of all completed items) / (maximum sum score of all possible items) × 100

Computation of AE-QoL Total Score

Example 1: All items were completed (maximum possible sum: 68 points)

Sum of all 17 completed items: 41 points

Total score = $100 \times (41/68) = 60$ (out of a possible 100 points)

Example 2: 2 items were not completed (maximum possible sum: 60 points)

Sum of all 15 completed items: 41 points

Total score = $100 \times (41/60) = 68$ (out of a possible 100 points)

Computation of Domain Scores (Example: Fears/Shame)

Example: Sum of all 6 completed items: 14 points

Maximum possible sum: 24 points

Domain Score = $100 \times (14/24) = 58$ (out of a possible 100 points)

Remarks

Since only answered items are included in the computation (and the calculated domain and total scores are not raw scores but linear transformations to a 0-to-100 scale), the calculated scores are not or only little influenced by missing items.

An AE-QoL domain score should not be calculated if more than one item is left unanswered in that domain. The AE-QoL total score should not be calculated if more than 25% of items

TP-GDO-WW-016-08 CONFIDENTIAL Project Document Version No. 2.0
Effective Date: 26 Nov 19 Project Document Effective Date: 13 Dec 2023
Related to: SOP-GDO-WW-019 Page 37 of 61

(>4 items) are left unanswered. For AE-QoL each derived domain score and total score, missing baseline or post-baseline handling are described in the Section 4.9.1.3.

The minimal and highest possible domain and total scores are 0 and 100, respectively.

AE-QoL total score, the change, and the percent change from baseline will be summarized by visit and treatment group.

The change from baseline in AE-QoL total score at Week 13 and Week 25 will be compared between ISIS 721744 80 mg every 4 weeks and pooled placebo using the MMRM model. The MMRM model will include effects of treatment, time, treatment-by-time interaction, baseline value at Study Day 1, and treatment-by-baseline interaction. Missing baselines will be imputed first by the average of available baselines across all patients in the FAS. The analysis will be conducted in the FAS. The unstructured covariance model will be used to model the within patient errors, shared across treatment and small sample adjustments to standard errors and tests will be made following the Kenward-Roger approach (Kenward and Roger 1997). If there are convergence problems with the repeated measures mixed model, this will be explored with the following methods in order: 1) the SCORING = 4 option could be used in the PROC MIXED statement in SAS. This makes SAS use Fisher scoring for the first 4 iterations. 2) If the convergence problem cannot be resolved, the unstructured covariance matrix will be replaced by the homogeneous compound symmetry covariance matrix (Type = CS in SAS).

The comparison between ISIS 721744 every 8 weeks and pooled placebo will also be analyzed in the same way as above mentioned.

The least-squares means, standard errors, and the 2-tailed 95% confidence intervals for the treatment group and placebo group will be presented.

Sensitivity Analyses

To evaluate the robustness of inferences made on MAR, a sensitivity analysis on FAS based on imputed data by using MI methods assuming J2R which is described in Section 4.9.1.3 will be performed. For each imputed data set, total score will be derived. The change from baseline in AE-QoL total score will be compared between ISIS721744 80 mg every 4 weeks and pooled placebo using ANCOVA with baseline as a covariate. Results will be combined using Rubin's rules.

In addition, a responder analysis will be performed for AE-QoL total score as an exploratory analysis:

A clinical response is defined as a \geq 6-point improvement from baseline in AE-QoL total score at Week 25, i.e., Post-baseline – Baseline \leq -6. The patient who archives a clinical response is a responder. Patients with non-missing response will be analyzed. The odds ratio, corresponding 95% confidence intervals and p-value will be provided by using a logistic regression model with the baseline, and the treatment-by-baseline interaction as covariates.

For patients who discontinued the Treatment Period early and started OLE, and patients who discontinued the Treatment Period early and were lost to follow-up before Week 25, the treatment termination reason will be checked. Due to reasons of adverse events or lack of efficacy, patients will be considered as a non-responder; due to other reasons, patient will be

CONFIDENTIAL

TP-GDO-WW-016-08 Effective Date: 26 Nov 19 Related to: SOP-GDO-WW-019 Project Document Version No. 2.0
Project Document Effective Date: 13 Dec 2023

categorized as missing and excluded from the analysis. Patient with missing baseline will also be excluded from the analysis.

Exploratory analysis for each AE-QoL domain score is described in Section 4.13.8.

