4.13.11.	3.11. Angioedema Activity Score (AAS)		
4.14.	Other Analyses	54	
4.15.	Determination of Sample Size	54	
4.16.	Changes in the Conduct of the Study or Planned Analysis	55	
5. REFER	ENCES	56	
APPENDI	X A. SAS SAMPLE CODES	57	
APPENDI	X B. EUROQOL-5-DIMENSIONS INDEX SCORE VALUESET FOR SAS	60	

REVISION HISTORY

Version No.	Effective Date	Summary of Major Changes
1.0	11 Apr 2022	New document
2.0	08 Dec 2023	Section 1: Updated the list of Study Protocol and Amendments.
		• Section 3.2.2 (and later related sections): Updated the primary analysis set from intent-to-treat (ITT) population to Full Analysis Set (FAS).
		• Section 3.2.5 (and later related sections): Added the following exploratory endpoints and analyses methods:
		 Change in each angioedema quality of life (AE-QoL) questionnaire domain scores
		 Time-normalized number of Investigator-confirmed HAE attacks from Week 17 to Week 25
		o Investigator-confirmed HAE attacks that involves the larynx
		• Section 4.2.2: Clarified baseline definitions with more details.
		• Section 4.9.1.3 (and later related sections): Angioedema Control Test (AECT) total score missing data handling is changed to LOCF in the main analysis. MI based on J2R will be a sensitivity analysis.
		• Section 4.9.1.4: Adjusted testing hierarchical rank.
		• Section 4.9.2.1: Added interaction of baseline and treatment group as a covariate in efficacy analysis models.
		• Section 4.9.2.6: Added typical patients as subgroup analyses.
		• Section 4.9.3 (and later related sections): Updated responder analyses methods by using a logistic regression instead of Chisquare. Added the analysis handling in case the logistic regression models with convergence issue.
		Section 4.9.3: Clarified continuous data analyses methods, i.e., mixed effects model with repeated measures (MMRM) or Wilcoxon Rank Sum test.

Project Document Version No. 2.0 TP-GDO-WW-016-08 CONFIDENTIAL Effective Date: 26 Nov 19 **Project Document Effective Date**: 13 Dec 2023 Related to: SOP-GDO-WW-019

ISIS 721744-CS5

LIST OF ABBREVIATIONS

Appreviation	Definition
ADA	Anti-Drug Antibody
AE(s)	adverse event(s)

AECT Angioedema Control Test AE-QoL angioedema quality of life ALP alkaline phosphatase

D @ ...

ALT alanine aminotransferase (SGPT) aPTT activated partial thromboplastin time AST aspartate aminotransferase (SGOT)

BUN blood urea nitrogen CRP C-reactive protein electrocardiogram

eCRF electronic Case Report Form EDC electronic data capture ER emergency room

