4.9.2.1. Primary Analysis

The primary efficacy endpoint will be tested by the following hypothesis:

```
H_0: \lambda_{ISIS 721744} / \lambda_{placebo} = 1 versus H_1: \lambda_{ISIS 721744} / \lambda_{placebo} \neq 1
```

 $\lambda_{ISIS\ 721744}$ refers to the Investigator-confirmed HAE attack rate from Week 1 to Week 25 in the ISIS 721744 80 mg every 4 weeks group and $\lambda_{placebo}$ refers to the Investigator-confirmed HAE attack rate during the treatment period in the placebo group. The null hypothesis is that the Investigator-confirmed HAE attack rate ratio from Week 1 to Week 25 is 1 (no difference between treatment groups), versus the alternative hypothesis that the Investigator-confirmed HAE attack rate ratio is not 1. Estimated attack rate ratios less than 1 would indicate that patients treated with ISIS 721744 80 mg every 4 weeks, on average, have a lower incidence of Investigator-confirmed HAE attacks from Week 1 to Week 25. The hypothesis will be tested using a Poisson regression model.

The primary analysis will be performed using a Poisson regression model and Pearson chi-square scaling of standard errors to account for potential overdispersion on the FAS. The model will include fixed effect for treatment group (categorical), baseline (the time-normalized run-in period attack rate, continuous), and the treatment-by-baseline interaction as covariates, and the logarithm of time in every-4-week that each patient was observed from Week 1 to Week 25 will be used as an offset variable.

All patients who discontinued the Treatment Period early and started OLE, and patients who discontinued the Treatment Period early and were lost to follow-up before Week 25, will have the time-adjusted attack rate included in the analysis.

The primary analysis will be performed based on the treatment policy strategy. Treatment effect will be estimated regardless of intercurrent events, which are defined in the Section 3.2.1.

From this model, the least squares mean rate, the standard error and the corresponding 95% confidence interval for each treatment group as well as, the model adjusted mean rate ratios of ISIS721744 80 mg every 4 weeks relative to the pooled placebo group and the corresponding 95% confidence interval will be estimated. These estimates will be reported as mean event rates per every-4-week by transforming the estimates using the exponential function. The p-value of the Wald-based chi-square test will be reported for testing the hypothesis.

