4.13.5. Change from Baseline in Patient Global Impression of Severity (PGIS) Scale

The PGIS scales will also be administered throughout the study for purposes of PRO validation and its use as an anchor for estimation of MID of other PRO measures. PGIS is a 1-item questionnaire rated on a 5-point scale (None = 1, Mild = 2, Moderate = 3, Severe = 4, Very severe = 5) designed to assess patient's impression of disease severity.

The number and percentage of patients of each scale will be summarized by visit and treatment group.

The change from baseline in PGIS will be summarized by visit and treatment group and be analyzed using Wilcoxon Sum Rank test.

The change from baseline in PGIS will also be dichotomized to category of "better" (change from baseline < 0) and "no change or worse" (change from baseline ≥ 0). The binary category data be summarized by visit and treatment group and be analyzed by using a logistic regression with baseline as the covariate.

Both analyses will be conducted in FAS.

TP-GDO-WW-016-08 CONFIDENTIAL Project Document Version No. 2.0 Effective Date: 26 Nov 19 Project Document Effective Date: 13 Dec 2023 Related to: SOP-GDO-WW-019 Page 50 of 61

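### Ranks 3, 4, 10 and 11 use a treatment-by-baseline logistic model, but the SAP does not say at which baseline or with which statistic treatment is tested, and the natural reading costs power

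*Combined protocol and SAP*

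**What the plan says.** - **Model.** SAP 4.9.3.3 obtains the odds ratio, its interval and the p-value "by using a logistic regression model with the baseline, and the treatment-by-baseline interaction as covariates". SAP 4.9.3.4 applies the same method to attack-free status. In the sequence of SAP 4.9.1.4 these are ranks 3 and 4 (every 4 weeks) and 10 and 11 (every 8 weeks). A non-significant result makes every lower rank exploratory.
- **Baseline.** It is defined as the run-in attack rate.
- **Odds ratio.** SAP 4.9.3.3 prints p1/(1-p1) divided by p2/(1-p2), where each p is an arm's responder proportion.
- **Statistic.** SAP 4.9.2.1 states "The p-value of the Wald-based chi-square test will be reported for testing the hypothesis", but for the Poisson primary test. Appendix A has LS-means code for the Poisson, negative binomial and repeated-measures models and no logistic code.
- **Fallback.** SAP 4.9.3 moves to Fisher's exact test if the logistic model does not converge, with one example (everyone in an arm responds).
- **History.** Protocol 10.6.3.2 planned chi-square or Fisher. The SAP Revision History for version 2.0 records "Added interaction of baseline and treatment group as a covariate in efficacy analysis models". SAP 4.16 justifies logistic regression by the greater power that baseline adjustment generally brings.
- **Other logistic analyses.** For the AECT main test, "the baseline and treatment-by-baseline interaction is not included for AECT", and there are no covariates at all. In the AECT sensitivity analysis "the logistic regression will include the baseline AECT total score (continuous) as a covariate". PGIS is analysed "by using a logistic regression with baseline as the covariate". The exploratory AE-QoL responder model does carry the interaction.

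**The concern.** With a treatment-by-baseline term there is no single treatment odds ratio. The p-value depends on the baseline at which the arms are compared and on the statistic used, and the SAP fixes neither for these four tests. The printed formula does not help, because a ratio of arm proportions is not a quantity this model estimates.

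The second problem is precision. With about 21 placebo patients and few expected placebo responders, the placebo slope on baseline is poorly estimated, and a Wald test at the mean baseline carries that uncertainty. Ranks 3 and 4 gate ranks 5-24, including every claim for the every-8-weeks regimen; ranks 10 and 11 gate what follows them.

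**Working it through.** **1. The plan's own figure.** SAP 4.15 states at least 90% power for the primary test with 54 patients (36 v 18) and 1.38 v 13.26 attacks per 6 months. Log rate ratio = ln(13.26/1.38) = 2.263. SE = √(1/(36×1.38) + 1/(18×13.26)) = 0.156, so z = 14.5 and power exceeds 0.999. With tenfold overdispersion SE = 0.493, z = 4.59 and power is 0.996. The figure is reproduced. No power is stated for ranks 3, 4, 10 or 11.

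**2. Why one p-value is not defined.** With logit(p) = β0 + β1·T + β2·B + β3·T·B, the log odds ratio at baseline b is β1 + β3·b, with variance V11 + 2b·V13 + b²·V33. Both change with b. The raw treatment coefficient is the case b = 0. Eligibility requires 2 attacks in at most 56 days, so the lowest possible baseline is 2/56 × 28 = 1.0 per 28 days.

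**3. Same data, different readings.**
- 32/42 v 6/21 responders (Fisher 0.0004): interaction-model Wald p is 0.49 at baseline 0, 0.12 at the lower quartile, 0.003 at the median and 0.0008 at the mean.
- 22/42 v 1/21 attack-free (Fisher 0.0002; treatment plus baseline, Wald 0.004). Baselines are set at gamma quantiles (shape 4, mean 3, floor 1.0), with active responders spread evenly. If the placebo responder has the 2nd lowest baseline, the interaction model gives 0.26 (Wald at mean), 0.42 (Wald at 0) or 0.000008 (likelihood ratio, LR, at mean). For the 3rd and 4th lowest, Wald at the mean gives 0.14 and 0.08. Of the 21 possible positions, 2 are separated; 16 of the other 19 give Wald-at-mean p below 0.05 (0.004-0.047).

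In simulated trials that converged, Wald at baseline 0 and at the mean fell on opposite sides of 0.05 in 63-77% (rank 3) and 24-43% (rank 10). Wald and LR at the mean disagreed in 21-44% at rank 4. Mean against median mattered less (0-21%).

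**4. Power.** The documents give no baseline spread, overdispersion or ≥70% responder rates. Assumed: gamma between-patient variance 0.25 or 1.0 before selection; run-in ending 3-7 days after the second attack (minimum 7 or 28 days) or at 56 days; drug-response variance 0 or 1; run-in-to-treatment variance 0 or 0.25. This gives 24 scenarios of 1,500 trials. Arms are 42 v 21, placebo mean 2.03 per 28 days, rate ratio 1.38/13.26 = 0.104, with Fisher on any separation.

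| Test of treatment | Stops at rank 3 or 4 |
|---|---|
| Interaction, Wald at mean | 0.4-43% (median 16%) |
| Interaction, LR at mean | 0-2.3% |
| Interaction, Wald at baseline 0 | 35-85% |
| Treatment plus baseline, Wald | 0.1-6% (median 1.2%) |
| Fisher alone | 0-2.5% |

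A smaller run (8 settings) gave 0.3-17% with the term (Wald at mean) and 0-2.3% without, hence the overall 0.3-43% v 0-6%. By run-in, Wald with v without the term gave 6-43% v 0.1-6% when randomisation follows soon after attack 2, as Protocol 6.1.1 instructs, and 0.4-13% v 0.1-2.1% with a full 56 days.

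At the rates in the plain-language results summary (0.44 v 2.26, ratio 0.195), stopping was 3-33% v 2-6% if drug response varies between patients. If it does not vary, both models stop often (40-67% v 34-67%) and the term adds 0-13 points.

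Rank 10 (21 v 21, ratio 1.02/2.26 = 0.45): power 45-92% with the term v 53-97% without, a loss of 2-17 points (median 5.5). Rank 11 loses 0-9 points.

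**5. No-effect rejection, ranks 3 / 4** (both arms at 0.3 or 0.5 times the placebo rate): interaction Wald 2.0-5.0% / 1.0-3.9%; interaction LR 6.0-8.5% / 1.5-8.4%; treatment plus baseline Wald 3.7-5.1% / 1.5-4.9%.

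**The case against.** - **The convention can be borrowed.** The SAP uses Wald for the primary test and LS-means in its code, so an analyst would naturally evaluate at the mean baseline. This makes the baseline-0 reading the least plausible, and its 35-85% should carry little weight. But SAP 4.9.3.3 does not refer to those sections, and the borrowed reading is the one that loses power.
- **Rank 4 usually escapes.** Separation sent 51-98% of simulated rank-4 trials to Fisher. Protocol 2.3.4 reports no attack-free placebo patient in phase 2; a repeat would remove the choice at that rank. This stands, but ranks 3 and 10 remain. The trigger also speaks only of non-convergence, so separation along baseline is left to interpretation.
- **Naming the contrast and statistic would be enough.** That cures the ambiguity, but not the Wald power loss. LR at the mean nearly removes the loss, yet rejected up to 8.5% with no effect.
- **The interaction was a deliberate version 2.0 choice, and SAP 4.16 compares with chi-square.** True. At rank 10 the interaction model's 45-92% is not uniformly below Fisher's 39-96%, so the rationale is not refuted. It supports baseline adjustment, which the simpler model keeps.
- **A choice after unblinding is constrained.** SAP section 1 has the plan finalised before database lock and later deviations documented. That limits a silent choice, but filling an unspecified contrast need not register as a deviation.

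**Conclusion.** The concern holds as a specification gap with a power cost. That the evaluation point, statistic and matching odds ratio are missing is a fact of the text and needs no simulation. The size does: roughly 0.3-43% v 0-6% for stopping at rank 3 or 4 at design rates, and about 2-17 points of power at rank 10. Both rest on the assumed baseline spread, run-in length and drug-response variation, so they show what can happen rather than a forecast.

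A reader might infer more than the documents support:
- **That baseline is undefined.** It is the run-in rate; the evaluation point is what is missing.
- **That false positives are inflated.** Under Wald they are not.
- **That one placebo responder typically overturns the result.** In the 22/42 v 1/21 example this happens only at the 2nd to 4th lowest baselines.
- **That the AECT main test is a precedent for treatment plus baseline.** It has no covariates; the AECT sensitivity analysis and PGIS are the precedents.
- **That the primary test is affected.** Ranks 1 and 2 use the Poisson model and are outside this point.

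**What to change.** Before unblinding, for ranks 3, 4, 10 and 11 and the other HAE responder thresholds (≥50%, ≥90%):

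1. Test treatment by Wald chi-square in a logistic model with treatment and run-in rate only. No evaluation point is then needed.
2. Define the reported odds ratio as the baseline-adjusted (conditional) one, and give crude proportions descriptively.
3. Apply Fisher's exact test on non-convergence or on complete or quasi-complete separation.
4. Add the logistic code to Appendix A and report the interaction as exploratory.

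The cost is SAP wording and one code block, with no new data. Effect modification by baseline becomes exploratory, and at ranks 3-4 this test may stop slightly more often than the protocol's Fisher test (up to 6% v 2.5%). In return it keeps the baseline adjustment and has 1-16 points more power than Fisher at rank 10 (53-97% v 39-96%).
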